12 REGULATORY AND ETHICAL APPROVALS

12.1 Statement of Compliance

Statement of compliance: The trial will be carried out in accordance with:

- The World Medical Association Declaration of Helsinki (1996) and the following updates Edinburgh (2000), Seoul (2008) and Fortaleza (2013)
- CTRC Standard Operating Procedures
- Principles of Good Clinical Practice
- The template content is structured consistent with the SPIRIT (Standard Protocol Item: Recommendations for Interventional Trials 2013)
- UK policy framework for health and social care research

12.2 Ethical Considerations

The trial will abide by the principles of the World Medical Association Declaration of Helsinki (1964) and the Tokyo (1975), Venice (1983), Hong Kong (1989) and South Africa (1996).

Potential ethical issues include informed consent where potential patient and carer participants will be identified by NHS clinicians providing their usual care and will avoid any coercion. Lack of mental capacity to give informed consent will be an exclusion criterion. Clinical equipoise exists for this trial because there is no evidence that the intervention improves patient outcome, so the trial team believe it is acceptable to randomise patients to the two treatment groups. The enhanced rehabilitation intervention is low risk as it consists of a workbook, diary and extra therapist time. The workbook does include examples of physical activities and exercises, and encourages patients to think about what they would like to achieve in consultation with their therapist, who will assess whether the goal is suitable and achievable. We will record safety events and take advice from the Independent Data and Safety Monitoring Committee (IDSMC) regarding the frequency of these, especially those deemed related to the intervention. The control group poses no additional risk to participants randomised to the control group as they will receive care as usual. The research officers will not only administer patient reported questionnaires at 17 and 52 week follow-up to maximise response rate, but also the SPPB. This has been designed to be administered in patients' homes and tests balance, gait speed and the ability to rise from a chair. The research officers will receive training in how to administer this safely, and will follow a lone worker policy.

Many of the frail elderly people that fracture their hip have cognitive impairment. Those who lack mental capacity to give informed consent are excluded from this RCT, however others with mild cognitive impairment or in the early stages of dementia are still eligible. The assessment of mental capacity is a clinical assessment which will be performed by clinicians on the orthopaedic wards. The following questions will need to be considered:

- Is the person able to understand the information relevant to the decision (to participate or not)?
- Is the person able to retain the information provided (which can be determined by a simple question of recall)?
- Can the person use or weigh that information as part of the process of making the decision (which can be assessed by inquiring of the person's understanding or potential options for participation)?
- Is the patient able to communicate his/her decision?

If the question is no to one or more of these questions, the patient will not be approached as they do not meet the eligibility criteria for inclusion in the trial. Also although the AMTS will not be used to determine eligibility, if the person has a low score then the clinician will be asked to re-assess capacity.

Some of the potential participants will initially be ineligible because of a temporary delirium. These people can be re-assessed several days later when the delirium has settled. The research team can maintain contact even if the patient is transferred to another ward for in-patient rehabilitation, or discharged home.

The mental capacity of participants may change. If the participant no longer has capacity when arranging a follow-up visit, no further data can be collected until the participant has been assessed as regaining capacity. Baseline data and other data collected up to that point will be used in the analysis.

Many of the participants can be classified as vulnerable adults. The clinicians and researchers in contact with them will have received statutory protection of vulnerable adults (POVA) training. This will be reported on a trial training log. A mechanism of immediate risk assessment and onward referral to appropriate authorities and police has been developed within the framework of the Human Rights Act 1998 and Data Protection Act 2018 if abuse or neglect is suspected, observed or disclosed by the participants.

12.3 Ethical Approval

Submission for NHS research ethics and NHS local governance approvals will be performed in the four months prior to the trial start date. All trial documentation, including PISC forms, template GP letters, and questionnaires will be submitted for approval. To conform to the Data Protection Act and Freedom of Information Act, all data will be pesudonymised and stored securely. No published material will contain patient identifying information.

12.4 Trial Discontinuation

In the event that the trial is discontinued all participants will complete their rehabilitation treatments as randomised. No further patients will receive the enhanced rehabilitation programme.

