9.4 Trial Closure

The end of the trial is defined to be the date on which data for all participants are locked and data entry privileges are withdrawn from the trial database. However, the trial may be closed prematurely by the Trial Steering Committee (TSC), on the recommendation of the Independent Data and Safety Monitoring Committee (IDSMC).

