10.6 Assessing "expectedness"

The assessment of expectedness will be performed by the Chief Investigator (or agreed delegate), not by the site research team.

All safety events assessed as "serious" and "related" will be assessed as expected and classified as RUSAEs if they meet the following criteria:

- Repeat fall during therapy sessions
- Repeat fracture during therapy sessions
- Other accident of injury during therapy sessions

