15.3.2 Trial Steering Committee (TSC)

The Trial Steering Committee will consist of an independent chairperson, 2 independent experts in the field of hip fractures and rehabilitation and an independent biostatistician. The role of the TSC is to provide overall supervision for the trial and provide advice through its independent Chairman. The

ultimate decision for the continuation of the trial lies with the TSC. Refer to the TSC terms of reference and trial oversight committee membership document for further details.

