15.3.3 Independent Data and Safety Monitoring Committee (IDSMC)

The independent Data and Safety Monitoring Committee (IDSMC) consists of an independent chairperson, plus 2 independent members who are experts in the field of hip fractures and rehabilitation.

The IDSMC will be responsible for reviewing and assessing recruitment, interim monitoring of safety and effectiveness, trial conduct and external data. The IDSMC will first convene prior to the start of recruitment and will then define frequency of subsequent meetings (at least annually). Details of the interim analysis and monitoring are provided in section 11 and 13.

The IDSMC will provide a recommendation to the TSC concerning the continuation of the trial. Refer to the IDSMC charter and trial oversight committee membership document for further details.

Name	Affiliations	Contribution to protocol
[name]	Department of Health Services Research, University of Liverpool	Chief Investigator
[name]	Clinical Trials Research Centre University of Liverpool Institute of Child Health Alder Hey Children's NHS Foundation Trust Liverpool	Head of Trial Management
[name]	Clinical Trials Research Centre University of Liverpool Institute of Child Health Alder Hey Children's NHS Foundation Trust Liverpool	Supervising Trial Manager
[name]	Clinical Trials Research Centre University of Liverpool Institute of Child Health Alder Hey Children's NHS Foundation Trust Liverpool	Senior Statistician
[name]	Clinical Trials Research Centre University of Liverpool Institute of Child Health Alder Hey Children's NHS Foundation Trust Liverpool	Senior Data Manager
[name]	Clinical Trials Research Centre University of Liverpool Institute of Child Health Alder Hey Children's NHS Foundation Trust Liverpool	Trial Co-ordinator
[name]	Site for Health Economics and	Health Economist

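### Section 12.4 tells sites to complete allocated treatment on any trial discontinuation, with no exception for a closure on safety grounds

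*Protocol*

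**What the plan says.** Section 12.4 consists of two sentences. The first covers people already in the trial: "In the event that the trial is discontinued all participants will complete their rehabilitation treatments as randomised". The second covers people not yet treated: "No further patients will receive the enhanced rehabilitation programme". Neither mentions the reason for stopping.

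Other sections describe how an early stop could come about:

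- Section 9.4: "the trial may be closed prematurely by the Trial Steering Committee (TSC), on the recommendation of the Independent Data and Safety Monitoring Committee (IDSMC").
- Section 15.3.3: "The IDSMC will be responsible for reviewing and assessing recruitment, interim monitoring of safety and effectiveness, trial conduct and external data".
- Section 12.2, on the safety events that the team logs, says it will "take advice from the Independent Data and Safety Monitoring Committee (IDSMC) regarding the frequency of these, especially those deemed related to the intervention".
- Section 15.3.2: the "ultimate decision for the continuation of the trial lies with the TSC".

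On hazard, section 3.2.5 accepts some risk of injury or falls during exercise but calls the package low risk. Section 10.6 names "Repeat fracture during therapy sessions" in its criteria for serious related events. Exercise is not confined to supervised sessions: "The workbook does include examples of physical activities and exercises" (section 12.2).

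**The concern.** Finishing allocated treatment is a sensible default when a trial stops for slow recruitment or lack of funds. Patients keep the rehabilitation they were promised, and nothing suggests that it harms them. The same default is wrong when the trial stops because the enhanced programme appears to cause harm. In that case 12.4, read literally, directs sites to go on delivering the programme to everyone allocated to it, and its only stop applies to new patients.

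What is at stake is the safety of enhanced-arm participants who are still in treatment at closure, and consistency of response across about 12 sites. Nothing in the sample size, the estimand or the analysis depends on it.

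**Working it through.** No figure in the protocol bears on this and there is nothing to calculate. The check is to read 12.4 against every section that might qualify it.

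**Step 1: scope of the rule.** The first sentence of 12.4 applies to all participants and to any discontinuation. The second stops new starts only. Between them, someone partway through the enhanced programme falls under the instruction to complete.

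**Step 2: is a safety closure foreseen?** Yes. Section 9.4 lets the TSC close the trial on the IDSMC's recommendation. Section 15.3.3 puts interim safety within the IDSMC's remit. Section 12.2 directs intervention-related events to it in particular. Section 10.6 shows that serious events arising in therapy sessions were considered.

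**Step 3: does another section supply the exception at trial level?**

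| Section | What it provides | Qualifies 12.4 for a safety closure? |
|---|---|---|
| 9.4 | Route to early closure | No; silent on treatment under way |
| 15.3.2 | TSC decides whether the trial continues | No; does not say what happens to sessions after closure |
| 15.3.3 | IDSMC remit; points to sections 11 and 13 for interim monitoring | No; neither section has a rule on ongoing treatment |
| 15.1, 15.3.1 | Sponsor and trial management group run the trial | They could issue an instruction; none is specified |
| 7.3 | Clinician may depart from allocation in the patient's interest; patient may withdraw | One patient at a time |
| 9.3.4 | Stop for withdrawn consent, intercurrent illness or a change in that patient's condition | One patient at a time; a trial-wide signal is not among the reasons |
| 8.3 | Up to six sessions, tailored to clinical need | One patient at a time; not a trial-level stop |

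**Step 4: apply the rule to the two kinds of closure.** For a recruitment or funding closure, 12.4 gives the right result. For a closure prompted by harm from the enhanced programme, it tells sites to complete that programme unless someone acts for the individual patient or a responsible body issues an instruction that departs from 12.4.

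**The case against.** The strongest reply is that nothing in 12.4 claims to override a safety decision. The harmful result requires the oversight bodies to close the trial for harm and then say nothing about sessions in progress, which is unlikely. The sponsor has overall responsibility (15.1), the trial management group runs the trial day to day (15.3.1) and the TSC supervises it (15.3.2). Related serious events must reach the coordinating unit within 24 hours (10.8.2). The TSC terms of reference and the IDSMC charter are cited but not shown, and they may settle the matter.

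Much of this stands, and it rules out a stronger reading. A reader might infer that in a safety closure there would be no trial-level decision and each clinician, therapist or patient would be left to choose. The documents do not support that, because bodies able to decide for the whole trial exist. Nor does 12.4 force a fixed number of further sessions on anyone, since 8.3 leaves number, timing and content to clinical need.

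What the reply does not remove is the wording. Section 12.4 is the protocol's own instruction to sites, and it is unconditional. A safety instruction from any of these bodies would have to depart from it. An exception that may be written in a charter does not correct the text that sites hold.

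**Conclusion.** The point holds as a badly fixed default. It is not a contradiction: 12.4 conflicts with no other section, but it lacks the one exception that the protocol's own closure route calls for. It is a minor patient-safety correction, worth considering and no more.

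The likelihood of a safety closure and the amount of harm cannot be estimated from the protocol. A reader might try to size the problem by counting enhanced-arm participants still within the delivery window at closure. Such a count would include people whose sessions have not begun or have already finished, and it says nothing about harm, so it should carry no weight.

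The conclusion assumes that 12.4 is read as written, and that no trial-level exception binds sites through a document not shown here. If the charter or terms of reference contain one, what remains is to bring 12.4 into line with it.

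**What to change.** Limit the first sentence of 12.4 to participants already randomised and add to it:

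> unless the TSC, on IDSMC advice, directs at closure that the enhanced sessions or workbook exercises stop or be paused for safety reasons; usual rehabilitation care continues in both arms, and sites check the usual-care referral of anyone whose sessions stop.

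Add a cross-reference in 9.4. Completion stays the default for every other kind of closure.

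The cost is one clause and one cross-reference, with no change to design, sample size or analysis. The downside is that some enhanced-arm patients may have little other community rehabilitation: sections 3.2.4 and 8.2 report that some feasibility-trial controls received none. Stopping sessions could leave such patients without therapy in mid-recovery, which is why the referral check is included. An automatic suspension of sessions is not advised. If the TSC decides at closure there is nothing left to suspend, and if it decides later, these same patients would lose therapy before anyone had judged that they should.

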13 DATA MANAGEMENT AND TRIAL MONITORING

Details of the monitoring to be carried out for the FEMuR III trial are included in the FEMuR III Trial Monitoring Plan. Trial Oversight Committees related to the monitoring of the trial are detailed in section 15.

13.1 Source Documents

Source data will be the hospital written and electronic medical records, community electronic and written records, audio-recordings and transcripts of qualitative interviews. The CRF will be considered the source document for data such as questionnaires where no prior record exists and which is recorded directly in the eCRF. Data collected (questionnaires, AEs and other data) will be transcribed into the remote electronic data capture system by the RPSO.

Date(s) of conducting informed consent process including date of provision of patient information, randomisation number and the fact that the patient is participating in a clinical trial (including possible treatment arms) will be added to the patient's medical record chronologically.

13.2 Data Capture Methods

For this trial quantitative data collected at each of the time points will be entered into a web-based data management system allowing controlled access to data by all sites with a full audit trail. The source electronic Case Report Forms (e-CRFs) in the web-based data management system is the primary data collection instrument for this trial and will have the design, format, derivation and validations used for each type of question documented in the Coding Specification.

The database will contain automatic validations and restrictions at the point of data entry to minimise data inconsistencies. A Data Management Plan (DMP) will be written and it will cover processes for receipt (SAE forms, consent forms), processing and storage of data.

The data will be reviewed periodically and data queries will be raised electronically on any missing, inconsistent or out of range data recorded in the database.

The data captured will be stored in a database running on servers maintained by the University of Liverpool. Access to the complete database will be limited to the core team members of the project involved in data management, data cleaning and analysis.

Audio recordings of qualitative data from interviews will be collected by the qualitative researcher and stored at the University of Liverpool.

Additional health service use data obtained from primary and secondary care records will be recorded electronically on encrypted laptop computers or collected by NHS staff on secure computers and anonymised in an electronic data set that is ready for secure transfer to the CTRC.

13.2.1 Data processing

All data requested on the eCRF must be entered. All missing data (not entered) will be queried. The database will be designed to allow sites to state whether a data item is not known or not applicable. Personnel at participating sites who are delegated the responsibility for entering data will be assigned unique usernames and passwords for the electronic system. An audit trial of all data entered into the system will be maintained which will log details of any changes made to the data. Data from patient completed questionnaires and demographic data at baseline, 17 weeks and 52 weeks follow-up assessments will be entered onto laptop computers by the RPSO administering the questionnaires. The original patient completed questionnaires will be stored securely at the site.

13.2.2 Central Monitoring

Data entered into the online system will be checked for missing or unusual values (range checks) and checked for consistency. Any suspect data will be queried within the online system. Data queries will be raised within the system by CTRC data management. Sites should respond to the queries providing an explanation/ resolution to the discrepancies and update the database where applicable. This process will take place within the electronic system and paper CRFs. There are a number of monitoring features in place at the CTRC to ensure reliability and validity of the trial data, to be detailed in the trial monitoring plan.

Screening and recruitment rates will be monitored by the Trial Management Group to identify and barriers to recruitment and discuss options to remove barriers if appropriate.

Completion and return rate of consent forms will be monitored at the CTRC to ensure valid consent has been obtained and consent forms are returned within the timeframes of the Trial Monitoring Plan.

13.2.3 Clinical Site Monitoring

In order to perform their role effectively, the trial coordinator, data manager (or monitor) and persons involved in Quality Assurance and Inspection may need direct access to primary data, e.g. patient records, laboratory reports, appointment books, etc. Since this affects the patient's confidentiality, this fact is included on the Parent Information Sheet and Informed Consent Form. During a site monitoring visit the trial coordinator, data manager (or monitor) and persons involved in Quality Assurance and Inspection may also review the Investigator Site File (ISF) to ensure all essential documents are present and the ISF is being maintained appropriately.

13.3 Confidentiality

Individual patient participant medical information obtained as a result of this trial is considered confidential and disclosure to third parties is prohibited with the exceptions noted below. Medical information may be given to the participant's medical team and all appropriate medical personnel responsible for the participant's welfare.

The CTRC will be undertaking activities requiring the transfer of identifiable data for both patient and carer participants.

- Verification that appropriate informed consent is obtained will be enabled by the provision of copies of participant's signed PISCs being supplied to the CTU by recruiting sites, which requires that name data will be transferred to the CTU.
- The RPSO will be responsible for co-ordinating the follow-up assessment of trial participants following discharge from hospital, and therefore will be required to receive contact details including name, address and telephone details.

This transfer of direct identifiers data is disclosed in the PISCs. The CTRC will preserve the confidentiality of participants taking part in the trial and The University of Liverpool is registered as a Data Controller with the Information Commissioners Office.

13.4 Quality Assurance and Control

The Trial Coordinator at the CTRC will verify appropriate approvals are in place prior to initiation of a site and the relevant personnel have attended trial specific training. A greenlight checklist will verify all approvals are in place prior to trial initiation at CTRC and the individual site.

The Trial Management Group (TMG) will determine the minimum key staff required to be recorded on the delegation log in order for the site to be initiated. The TMG will also monitor the screening, randomisation and consent rates between sites.

The trial will be conducted in accordance with procedures identified in the protocol. Independent oversight of the trial will be provided by the Data and Safety Monitoring Committee and independent members of the Trial Steering Committee.

The PI and other key staff from each site will attend site initiation training, coordinated by the CTRC, which will incorporate elements of trial-specific training necessary to fulfil the requirements of the protocol. Site staff will receive an on-site training visit by the trial co-ordinator and CI (if available) before green light to begin recruitment is give. The site training visit will consist of a review of the trial protocol, recruitment, consent, randomisation, follow-up, trial procedures, safety event reporting, intervention, trial arrangements, data protection and data handling.

Data will be evaluated for compliance with the protocol and accuracy in relation to source documents. The process for consent, recruitment and randomisation will be evaluated for compliance with the protocol. Data quality checks and monitoring procedures will be undertaken in line with the trial Data Management Plan;

Full details of data evaluation can be found in the trial Data Management Plan

